## 4.3.4. ZIKV Infection Clinical Management and Follow-Up

There is no curative treatment for ZIKV infection. In both **Part A** and **Part B**, study sites should have plans for subjects to have access to clinical care and management of ZIKV infection based on recommendations by CDC, WHO, and/or site local authority. Subjects should continue to participate in VRC 705 follow-up visits while under care. Study staff must document all signs and symptoms of infection and all clinical care provided.

Any subject with a positive ZIKV result must be discontinued from receiving study product. In addition, pregnancy testing and pregnancy prevention counseling must be added to all study visits for female subjects of childbearing potential following a ZIKV diagnosis, as shown on Tables B and C in the Schedule of Evaluations.

In areas where there is an option, per PI discretion, it is acceptable for a ZIKV-infected study subject to co-enroll in a concurrent study of treatment or management of ZIKV infection to allow for optimal care of the subject. The IND Sponsor should be notified if co-enrollment occurs. Treatment procedures and co-enrollments will be documented in the study database and available to the Protocol Safety Review Team (PSRT) through study reports. With permission from the subject, the results of diagnostic testing and other evaluations conducted for this study may be shared with the clinician(s) providing the medical care to minimize the need for the subject to have extra blood draws or repeat testing.

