# 6.4. Statistical Analysis

Study accrual is defined in this protocol as being randomized to a treatment group and receiving the first administration of study product. All accrued subjects will receive at least one product administration and therefore will provide some safety data. The safety population will include all enrolled subjects, summarized according to the actual vaccination dose received.

In **Part B**, all subjects will be tested for baseline ZIKV serostatus based on samples collected at Visit 02 prior to the first product administration. Since those with prior exposure to ZIKV may respond differently to the vaccine from those naïve subjects, safety, immunogenicity and efficacy will be analyzed within each stratum defined by baseline ZIKV status in addition to overall strata combined. **Part A** of the study is to be conducted at endemic or potentially endemic sites with baseline ZIKV serostatus tested, then safety and immunogenicity analyses will be similarly run by stratum in addition to overall strata combined.

Three types of analysis cohorts are defined. The Intent-to-treat (ITT) cohort will include all accrued subjects according to group assignment. The Per Protocol (PP) cohort will include all subjects receiving all planned vaccinations within window as assigned by the randomization schedule, and not experiencing any other major protocol deviations prior to the visit of

evaluation. The Modified intent-to-treat (mITT) analyses will include all accrued subjects who remain event-free one week after all planned product administration, where event is the primary efficacy event of a positive ZIKV PCR test result.

No multiple comparison adjustment will be employed for safety, immunogenicity, or efficacy analyses. Missing data will be primarily considered as missing completely at random in safety and immunogenicity analysis provided missing data is modest (e.g. <5-10%). For completeness, we will examine the missing data completely at random assumption and perform sensitivity analyses which weaken the missing completely at random assumption if the missing data is >10% or if the missing at random assumption is questionable. For efficacy, missing at random will be assumed and methods for handling missingness, such as multiple imputation and inverse propensity weighting, will be considered.

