# 6.4.6. Randomization of Treatment Assignments and Unblinding Criteria

Randomizations will be done online using an electronic randomization system. The randomization code will be prepared by the Protocol Statistician and included in the enrollment module for the trial. The randomization code will link to the treatment assignment. The electronic data system will assign each subject a randomization code after eligibility has been confirmed in the system.

In **Part A**, randomization will be performed with 1:1:1 allocation to the three vaccination arms at each study site. In **Part B**, randomization will be performed with 1:1 allocation to the ZIKV DNA vaccine and placebo at each study site.

**Part A** will be open-label and no unblinding will be needed. In **Part B**, the injections will be prepared by an unblinded site pharmacist, designee, or otherwise qualified personnel who will not be involved in any subject assessments and who will not discuss randomizations with blinded study staff. The subjects, the study personnel who perform product administrations and

assessments, data entry personnel at the sites, and laboratory personnel performing immunologic assays will be blinded to the treatment assignment of all product administrations. Product assignments will be provided to the site PI at completion of the study per the Study Blinding Plan for communication to the study subjects. The DSMB may receive data in aggregate and presented by treatment group, but without the treatment group identified. The DSMB may be unblinded to individual study treatment assignments, as needed, to adequately assess safety issues.

The IND Sponsor intends to unblind treatment assignments for **Part B** of the study once 90 cases of ZIKV infection are detected. The DSMB will be consulted prior to unblinding.

If necessary, the site PI or designee and Protocol Chair may agree that an event, such as management of an AE or pregnancy, requires emergency unblinding of an individual subject's assignment. If early unblinding occurs for any reason, it will be documented as a protocol deviation. The Protocol Statistician, the site IRB/EC (as required), and the DSMB will be notified that an early unblinding has occurred and provided with a statement explaining the medical necessity for the early unblinding.

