### 6.2. Timing of Analyses

- 1. Interim immunogenicity analyses for **Part A** may be performed on an ongoing basis, per sponsor directive.
  - a) The first interim immunogenicity analysis will be performed when 10 subjects in each group have data available through Visit 05
- 2. Interim immunogenicity analyses for **Part B** may be performed on a subset of subjects after the NAb assays up to and including Week 12 have been completed for the subset of subjects.
- 3. Final Efficacy Analysis will occur when the total number of mITT virologic ZIKV cases (primary efficacy endpoint) in **Part B** of the study reaches 90 or study completion.
- 4. The Final Analysis of safety data for both Part A and Part B will be performed after clinical database lock when all subjects have been followed through 32 weeks after the last product administration for Part A and at least 6 months after the first product administration for Part B. Final analysis of the efficacy and immunogenicity endpoint data will follow the database lock of the immunogenicity and efficacy data once all lab data are received and validated.
- 5. Exploratory Immunogenicity Analyses may be completed following database lock as assay results become available.

For all analyses completed prior to database lock, individual subjects' study group assignments will not be unblinded with the possible exception of a review of selected AEs or episodes of ZIKV disease for safety monitoring requirements, as described in the Study Blinding Plan.

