#### 6.3. Analysis Populations

The two parts of the study share the following definition for each type of analysis population:

All Enrolled Subjects: all subjects who enrolled in the screening segment. This population will be used for summaries of subject disposition, eligibility, demographics and the serious adverse event listing.

**Safety population**: all randomized subjects in the study who receive at least one study product administration, and have at least one post-administration safety assessment, analyzed according to the study product received. If it is unknown what study product was received, subjects will be summarized according to the randomized treatment assignment. This population will be used for analysis of all safety endpoints.

The **Intent-to-treat (ITT)** population will include all randomized subjects, analyzed according to the randomized study product. The ITT population will be used to analyze immunogenicity and efficacy analyses.

The **Modified intent-to-treat (mITT)** analyses will include all randomized subjects who remain event-free one week after all planned product administrations, where event is the primary efficacy event of a positive ZIKV PCR or other Zika test result with or without symptoms, analyzed according to the randomized study product. The mITT population will be used for immunogenicity and efficacy analyses (**Part B** only).

The **Per Protocol (PP)** analyses will include all subjects receiving three administrations within window as assigned by the randomization schedule, and not experiencing any other major protocol deviations prior to their week 12 visit. Safety, immunogenicity, and efficacy analyses will all be examined for the PP population. The following subjects will be excluded from the PP population:

- Subjects who do not receive 3 administrations of study product.
- Subjects who acquire confirmed ZIKV infection on or before 1 week after third administration.
- Subjects missing baseline ZIKV serostatus.
- Subjects who received a study product administration different from the randomization assignment.
- Subjects who receive the second or third administration out of the protocol-defined windows:
- Subjects who did not meet all inclusion/exclusion criteria at the time of enrollment.
- Subjects whose study group assignment is unblinded during study follow-up (Part B).
- Subjects who receive study product via incorrect route or incomplete administration.

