- For efficacy analyses subjects who do not have at least one post-administration efficacy assessment (at least one visit or PCR (or other Zika) result) following product administration 3.
- *For immunogenicity analyses* subjects who do not have NAb results 4 weeks post product administration 3 (Visit 05) or at baseline.
- For immunogenicity analyses subjects with serum sample for 4 weeks post product administration 3 (Visit 05) collected outside the protocol specified window (Day 77 to Day 91).

Subjects may be censored from the Per-Protocol Analysis for any of the following:

- Receipt of any non-study inactivated vaccination within 2 weeks of any study product administration.
- Receipt of any live attenuated vaccination within 4 of any study product administration.

- Receipt of any other investigational research agent at any time during the trial.
- Receipt of any concomitant medication that may interfere with immune response, including but not limited to:
  - Any systemic immunosuppressive or cytotoxic medical blood products within 16 weeks prior to randomization.
  - Immunoglobulin within 8 weeks prior to randomization.
  - Current anti-TB prophylaxis or therapy.
- Confirmed or suspected immunosuppressive or immunodeficient condition, including HIV infection.

All exclusions from analysis populations and censoring events will be reviewed by the Protocol Statistician, Protocol Chairs, and Lead Medical Officer and others on the Protocol Safety Review Team.

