#### **10.2.** Analysis of vaccine efficacy:

The time of ZIKV events is defined as the illness onset date recorded on the ZIKV Endpoints eCRF (for clinical cases) or date first specimen was collected with a positive PCR or other Zika result, whichever is earliest. Time to event for analysis will be as follows:

- For subjects with infection: time of ZIKV event minus date of first administration (Visit 02) + 1.
- For subjects with no infection: date of protocol completion/termination as recorded on the study status eCRF minus date of first administration (Visit 02) + 1. These subjects will be censored at their date of study completion or date of early termination.
- Subjects with or without infection may be censored from the analysis for the PP population as described in Section 6.3.

For subjects who were randomized but did not receive any product, date of randomization will be used in place of date of first administration in the definitions above.

The cumulative incidence of ZIKV cases will be presented graphically as 1 – Kaplan-Meier curves. Curves will be presented by study group and baseline ZIKV stratum and by study group combined over all subjects (Figure 27 through Figure 44, Appendix 2). Similar presentations will be displayed for virologic ZIKV cases and subclinical ZIKV cases).

Vaccine efficacy will be estimated as 1 - Hazard Ratio estimated from a Cox proportional hazard model. The primary efficacy analysis for ZIKV infection will use the following test:

H0: VE 
$$\leq 20\%$$
  
H1: VE  $\geq 20\%$ 

The criterion for success will be that a one-sided test of  $H_0$  has p-value  $\leq 0.025$ . Success will be met if the lower bound of the 95.0% confidence interval for VE estimated for the mITT population using a Cox proportional hazards model stratified by baseline ZIKV status is >20 (Table 51 through Table 53, Appendix 1).

If the null hypothesis VE  $\leq 20\%$  is not rejected, then the following will be tested using a one-sided type I error rate of 0.025.

H\*0: VE =0% H\*1: VE >0%

As secondary analyses of vaccine efficacy this hypothesis will be tested for:

- ZIKV cases without stratification for baseline ZIKV serostatus
- virologic ZIKV cases stratified by baseline ZIKV serostatus
- subclinical ZIKV cases stratified by baseline ZIKV serostatus
- subclinical ZIKV cases without stratification for baseline ZIKV serostatus

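### The per-protocol unblinding exclusion has no date limit, so it can remove some ZIKV endpoint events because they occurred; the investigational-agent censoring rule gives no censoring date

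*Combined protocol and SAP*

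**What the plan says.** The mandatory PP exclusions in SAP 6.3 include "Subjects whose study group assignment is unblinded during study follow-up (Part B"). The whole subject is excluded, and the item carries no time limit other than follow-up itself. The PP definition above that list is limited in time: it requires subjects "not experiencing any other major protocol deviations prior to their week 12 visit". Protocol 6.4 uses a different limit, "not experiencing any other major protocol deviations prior to the visit of" evaluation. Protocol 6.4.6 makes unblinding a deviation: "If early unblinding occurs for any reason, it will be documented as a protocol deviation". It allows emergency unblinding for reasons such as an adverse event or pregnancy, and states the sponsor's intention to unblind Part B once 90 cases are detected.

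SAP 6.2 says individual assignments stay blinded in analyses before database lock, "with the possible exception of a review of selected AEs or episodes of ZIKV disease for safety monitoring requirements", and refers to the Study Blinding Plan for details.

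A second list in SAP 6.3 gives reasons why subjects may, not must, be censored from the PP analysis. One is "Receipt of any other investigational research agent at any time during the trial". Under Protocol 4.3.4, "it is acceptable for a ZIKV-infected study subject to co-enroll in a concurrent study of treatment or management of ZIKV infection". SAP 10.2 adds: "Subjects with or without infection may be censored from the analysis for the PP population as described in Section 6.3". Neither SAP section gives a censoring date. SAP 10.2 runs every efficacy analysis in the ITT, mITT and PP populations.

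**The concern.** A PP exclusion should rest on facts that precede the outcome, or should end follow-up at a stated date. The unblinding item does neither. Because a ZIKV episode can itself prompt unblinding, membership of the PP population can depend on having had the endpoint. The agent rule raises the same question in a weaker form, since joining a ZIKV treatment study is open only to infected subjects and follows infection.

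At stake is the reading of the PP efficacy result as support for the primary one. Losing cases equally from both arms costs PP events and precision. Losing them unequally also shifts the PP estimate of VE, in either direction.

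The 90-case unblinding adds a second problem. SAP section 10 repeats the efficacy analysis if further cases are reported before lock. On a literal reading, everyone still in follow-up at the sponsor-wide unblinding would by then have been unblinded during follow-up.

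**Working it through.** **Order of events.** SAP 10.2 dates a ZIKV event at illness onset or first positive specimen, whichever is earlier. Unblinding to review that episode, or co-enrolment after diagnosis, must therefore come later.

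- Unblinding: event, then unblinding, then whole-subject exclusion under SAP 6.3. The event is lost.
- Other agent: event, then agent, then possible censoring. The event counts if follow-up stops at the agent date. It is lost if censoring means removal or an earlier date. The SAP does not say which.

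**The plan's own figure.** Protocol 6.3.2.3 gives 90% power at 90 cases for VE 61% against a null of VE ≤ 20%. A case falls in the vaccine arm with probability (1 − VE)/(2 − VE):

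- null p0 = 0.80/1.80 = 4/9
- alternative p1 = 0.39/1.39 = 0.2806
- z = [√90 × (0.4444 − 0.2806) − 1.96 × √(p0(1 − p0))] / √(p1(1 − p1)) = 1.29, so power = 90.2%

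The stated figure reproduces. An exact binomial test gives 89.0%.

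**Equal removal in both arms (assumed shares).** The expected case split, and so VE, stays at 61%; only events are lost.

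| Share removed | Cases left | PP power |
|---|---|---|
| 0% | 90 | 90.2% |
| 5% | 86 | 88.8% |
| 10% | 81 | 86.8% |
| 20% | 72 | 82.3% |
| 30% | 63 | 76.6% |

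Ninety cases is a reference point. PP will start lower for its other exclusions.

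**Unequal removal (assumed shares).** With fv of vaccine cases and fp of placebo cases removed, apparent VE = 1 − (1 − VE)(1 − fv)/(1 − fp).

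| True VE | fv | fp | Apparent PP VE |
|---|---|---|---|
| 61% | 20% | 10% | 1 − 0.39 × 0.8/0.9 = 65.3% |
| 61% | 20% | 0% | 1 − 0.39 × 0.8 = 68.8% |
| 61% | 0% | 20% | 1 − 0.39/0.8 = 51.2% |
| 20% | 20% | 10% | 1 − 0.80 × 0.8/0.9 = 28.9% |

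In the last row, the chance of rejecting VE ≤ 20% in the PP analysis is 7.2% instead of 2.5%.

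**In whole cases.** At VE 61%, 90 cases split as 90 × 0.2806 ≈ 25 vaccine and 65 placebo. Take VE = 1 − v/p and SE of log(v/p) = √(1/v + 1/p):

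- 25/65: VE 61.5% (95% CI 39.0 to 75.8)
- 23/65: VE 64.6%
- 20/65: VE 69.2% (49.2 to 81.4)
- 25/60: VE 58.3%

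**The case against.** The case against has several parts.

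- **The time limits may govern.** Early unblinding is a protocol deviation, and both PP definitions limit deviations in time. Read that way, unblinding after week 12 because of a later case does not exclude. This is a fair reading of intent, but the listed item says follow-up without qualification and the two limits differ from each other. The texts need reconciling.
- **Censoring normally keeps earlier events.** In a time-to-event analysis the ordinary reading stops follow-up at the agent date, so a case that preceded co-enrolment counts. The rule is also discretionary, co-enrolment is optional, and a management study need not give an agent. This stands: the defect here is a missing date, not a stated deletion.
- **Unblinding for a ZIKV episode is only a possible exception.** Its details sit in the Study Blinding Plan, which is not among the documents. Access by a restricted safety group may not count as the subject being unblinded. That is unresolved, and the SAP should say.
- **Unblinding may mean individual unblinding only.** SAP 7.1 points to the subject-level deviation listing for unblinded subjects, which supports this. The sponsor-wide problem is then one of wording, but the words still need changing.
- **Few cases are exposed.** Subclinical cases come from retrospective testing, subjects are not told those results, and the analyses using them follow database lock. Those results cannot prompt unblinding or co-enrolment. This stands.
- **Exclusions are reviewed.** SAP 6.3 requires review by the Protocol Statistician, Chairs, Lead Medical Officer and safety review team. It does not say that the review is blind to arm or outcome.

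**Conclusion.** The concern holds for the unblinding item: as written, it can remove some PP endpoint events because they occurred. For the agent rule, what holds is that the fate of an earlier event is undefined. The effect is confined to PP efficacy. No success criterion uses PP, and the primary mITT analysis is untouched. The point is worth correcting but does not threaten the trial's main conclusion.

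The size is unknown. Every removal share and case count used above is an assumption; the calculations show only how PP power and VE respond.

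A reader might infer more than the documents support:

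- That both rules force cases out. Only the unblinding exclusion is mandatory.
- That cases are removed while non-cases are always kept. Non-cases can be unblinded for an adverse event or pregnancy, and can take another agent. What is specific to cases is the route through a ZIKV episode.
- That PP VE is inflated. Bias needs removal to differ by arm. Subjects and site assessors are blinded, so episodes cannot be picked for review as vaccine breakthroughs before the arm is known. If severity drives review and the vaccine attenuates illness, more placebo cases would go and PP VE would fall.

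**What to change.** Amend SAP 6.3 and 10.2 to state that:

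1. the unblinding rule applies to individual unblinding, not the planned sponsor-wide unblinding, and whether access by a restricted safety group counts;
2. PP follow-up is censored at the date of individual unblinding or of first receipt of another investigational agent;
3. any ZIKV event dated, by the SAP 10.2 definition, on or before that trigger is kept.

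Reconcile this with the week 12 limit in the SAP and the visit-of-evaluation limit in the protocol.

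The cost is SAP wording and PP programming, best settled before lock and unblinding. Unblinding is already documented as a deviation, and the deviation listings carry study day. The agent date is less certain. Co-enrolment is recorded, but the ZIKV endpoint listing shell has a co-enrolment field and no date. Protocol 4.4 updates concomitant medications in the database only for adverse events needing expedited reporting or new chronic conditions. Confirm that the start date of the agent or co-enrolment is captured, and query sites for the subjects concerned if it is not.

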## 4.2.6. Follow-Up Visits and Scheduling

Study follow-up will continue via clinical visits after the first product administration through 32 weeks in **Part A** and 96 weeks in **Part B**. Clinical visits may include a health status review, vital signs and/or blood collection. The scheduled visits are based on intervals of time after each product administration visit. If study product is not given as scheduled, then the follow-up visits should be scheduled based on the date that the last study product was given. When product is not given, the corresponding follow-up phone contact (A visit) may be omitted.

The schedule of visits, allowable windows (range of consecutive days) for completing the visits, terms of rescheduling visits, and evaluations performed at each visit are shown in the tables in Appendix III. After Visit 02, deviations from the visit windows are discouraged and will be recorded as protocol deviations but are permitted, at the discretion of the IND Sponsor.

As of protocol version 5.0 approval, study visits 15, 17, 19, 21, 23, and 25 will not be performed. The applicable study visits have been removed from the Schedule of Evaluations table for Part B (Appendix III).

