## 4.2.6.1. Important Information about Shifting Study Visits

Study visits are scheduled a specific number of days apart in order to obtain blood samples for safety and research data at critical time points after each product administration. Note that these days are calendar days and not working business days. Therefore, the "Day of Study" is important to consider when scheduling or rescheduling a subject visit. All study visits are scheduled based on the date of the most recent product administration. Below is further explanation on scheduling.

Visit 02 (Day 0) = first product administration visit. Study Visits 02A and 03 must be scheduled based on the date of the first product administration.

Visit 03 = second product administration visit. Study Visits 03A through 04 must be scheduled based on the date of Visit 03. For example, if Visit 03 occurs +15 calendar days outside of the visit window, then Visits 03A and 04 must also be moved ahead +15 calendar days. If the second product administration does not occur, then schedule all follow-up visits based on the date of the first product administration.

Visit 04 = third product administration visit. Study Visits 04A through 26 must be scheduled based on the date of Visit 04. For example, if Visit 04 occurs +20 calendar days outside of the visit window, then visits 04A through 26 must also shift (or be moved forward) +20 calendar days. If the third product administration does not occur, then schedule all follow-up visits based on the date of the second product administration.

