CBC with differential	EDTA	3		3		3	3		3	3	3				
ALT	SST	4		4		4	4		4	4	4				
Research Samples															
Serum	SST	40		16		16	16		16	16	16	16	16	16	16
 PBMC and plasma	EDTA	[40]		[40]		[40]	[40]		[40]	[40]	[40]	[40]	[40]	[40]	[40]
Daily Volume (mL)		87	-	63		63	63	-	63	63	63	56	56	56	56
Cumulative Volume (mL)		87	87	150	150	213	276	276	339	402	465	521	577	633	689

administrations must be at least 21 days apart). Schedule Visit 02A relative to Visit 02, Visit 03A and 03B relative to Visit 03, Visits 04A through 10 relative to Visit 04, if all product administrations are given as scheduled. Refer to Section 4.2.6.1 for scheduling instructions if all product administrations are not given as scheduled. Visits windows: Visits 02A, 03A, 04A (+3 days); Visits 03B and 04B (±2 days); Visits 03, 05, 06, 07, 08, 09, 10 (±7 days); Visit 04 (-7 days; product

 Targeted physical examination is only performed as needed, based on subject report or other indications of illness; brackets [] indicate optional, as needed.

 Pregnancy prevention counseling and pregnancy testing are to be added to every visit, as shown in brackets [], for any subject of childbearing potential with confirmed ZIKV infection. A pregnancy test and pregnancy prevention counseling are not required for women determined to be of non-reproductive potential or for men throughout the study.  Brackets [] indicate that only approved sites will collect samples for PBMC and plasma storage. Tube types/volumes are shown to estimate blood volumes in mL.

 Different tubes for clinical evaluations may be used to meet site requirements but research sample tubes must be used as shown or as instructed by the IND Sponsor.

_
$\circ$
Ś.
/ersion
-
705,
Q
Ř

$\infty$	
-	
$\circ$	
$\sim$	
•	
$\infty$	
$\sim$	
÷	
S	
5	
 	
2	
_	

I

		TABI	LE C: S	CHEDI	JLE OF	EVALU	ATION	S – PAR	T B						
Visit Number		02	02A	03	03A	04	04A	05	90	07	08	60	10	11	12
Week of Study		0M	W1	W4	W5	W8	6M	W12	W16	W20	W24	W28	W32	W36	W40
Day of Study		D0	D7	D28	D35	D56	D63	D84	D112	D140	D168	D196	D224	D252	D280
Clinical Evaluations	eduD9														
 Medical History Review		х		х		х		Х	х	х	х	х	х	х	Х
Vital Signs		Х		Х		Х			Х						
 Targeted Physical Examination		[X]		[X]		[X]		[X]	[X]	[X]	[X]	[X]	[X]	[X]	[X]
 Pregnancy Prevention Counseling		Х		Х		Х		[X]	[X]	Х	[X]	[X]	[X]	[X]	[X]

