 Pregnancy Test		х		х		х		[X]	[X]	х	[X]	[X]	[X]	X	[X]
Eligibility Confirmation		х													
Randomization		Х													
Product Administration		Х		Х		Х									
Begin Diary Card		Х		Х		Х									
Phone Contact (clinic visit if needed)			Х		Х		Х								
CBC with differential	EDTA	3		3		3			3						
ALT	$\mathbf{SST}$	4		4		4			4						
Research Samples															
Serum	$\mathbf{SST}$	32		16		16		16	16	8	8	8	8	8	8
 PBMC and plasma	EDTA	[40]		[40]		[40]		[40]	[40]						
 Whole blood (red blood cells and plasma)	EDTA	10		10		10		10	10	10	10	10	10	10	10
Daily Volume (mL)		89	•	73		73		66	73	18	18	18	18	18	18
Cumulative Volume (mL)		89	89	162	162	235	235	301	374	392	410	428	446	464	482
'isit windows: Visits 02A, 03A, 04A (-	+3 davs):	Visits (	3.05.0	0.07.0	8, 09, 10	0.11.12	(±7 da	vs): Vis	it 04 (-7	davs/+	14 davs:	product	t admini	strations	must

be at least 21 days apart). Schedule Visit 02A relative to Visit 02A relative to Visit 03, Visits 04A through 26 relative to Visit 04, if all product administrations are given as scheduled. Refer to Section 4.2.6.1 for scheduling instructions if all product administrations are not given as scheduled. Full medical history review at screening, then perform an interim medical history review from V02 through end of study.

 Targeted physical examination is only performed as needed, based on subject report or other indications of illness; brackets [] indicate optional, as needed.

 A pregnancy test and pregnancy prevention counseling are not required for females of non-childbearing potential or for men throughout the study. Pregnancy prevention counseling and pregnancy testing are to be added to every visit, as shown in brackets [], for any subject of childbearing potential with ZIKV infection.

 Brackets [] indicate that only approved sites will collect samples for PBMC and plasma.

Scheduled collection of whole blood and serum research samples to evaluate asymptomatic ZIKV infection can occur outside of visit windows without permission but should be recorded as a protocol deviation. Every effort should be made to obtain these samples once a month.

 Tube types/volumes are shown to estimate blood volumes in mL. Different tubes for clinical evaluations may be used to meet site requirements but research sample tubes must be used as shown or as instructed by the IND Sponsor.

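### The per-protocol serum window is fixed at study Days 77–91, but the protocol counts Visit 05 from the actual third dose, so compliant sera can be excluded

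*Combined protocol and SAP*

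**What the plan says.** SAP 6.3 lists, among the exclusions for PP immunogenicity, subjects with a "serum sample for 4 weeks post product administration 3 (Visit 05) collected outside the protocol specified window (Day 77 to Day 91"). The same section separately excludes subjects whose second or third dose was out of window. It adds that "All exclusions from analysis populations and censoring events will be reviewed by the Protocol Statistician, Protocol Chairs, and Lead Medical Officer" and others on the safety review team.

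The protocol anchors its visits differently. Section 4.2.6 says that "The scheduled visits are based on intervals of time after each product administration visit". Section 4.2.6.1 says that "Study Visits 04A through 26 must be scheduled based on the date of Visit 04", and gives an example: "if Visit 04 occurs +20 calendar days outside of the visit window, then visits 04A through 26 must also shift". The Appendix III footnotes repeat the anchor for Part A ("Visits 04A through 10 relative to Visit 04, if all product administrations are given as scheduled") and Part B ("Visits 04A through 26 relative to Visit 04, if all product administrations are given as scheduled"), and allow Visit 05 ± 7 days. SAP 9 also defines the immunogenicity time point as four weeks after the third administration.

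On a separate, minor point, the Table 7 shell (reused for Table 8) restricts the early-infection exclusion to symptomatic cases. SAP 6.3 makes no such restriction.

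**The concern.** The exclusion criterion has two halves: the protocol's window, and a pair of day numbers said to be that window. They coincide on only one dose-3 date. On any other permitted date they select different subjects, and the SAP does not say which half governs.

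Whether a compliant subject enters the PP analysis of neutralizing antibody would then depend on the calendar day of dose 3 and not on compliance. The rule also errs in the other direction: after a late dose 3, a serum drawn well short of four weeks passes this criterion as the four-week sample. Two programmers could build different PP sets from the same text, which a pre-specified population is meant to prevent.

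**Working it through.** **Inputs.** From Appendix III: Visit 03 (dose 2) is nominally Day 28 ± 7, Visit 04 (dose 3) Day 56, and Visit 05 Day 84 ± 7, with doses at least 21 days apart. The Part B Visit 04 window is −7/+14 days, read from damaged table text. The plus side of the Part A Visit 04 window is not legible, so the sizes below are for Part B only; the anchoring mismatch is the same in Part A.

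**The SAP's own figure.** Day 84 ± 7 gives Days 77–91. The SAP range is therefore the nominal window counted from Day 0.

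**The protocol's window.** With dose 3 on day d, Visit 05 is due on d + 28 ± 7, that is d + 21 to d + 35: 15 permitted days.

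**Overlap.** The number of those 15 days that also lie in Days 77–91 is 15 − |d − 56|, with a floor of 0.

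| Dose 3 (d) | Permitted Visit 05 days | Kept by the SAP rule | Exact 4-week serum (d + 28) |
|---|---|---|---|
| 49 | 70–84 | 8 of 15 | Day 77, kept |
| 56 | 77–91 | 15 of 15 | Day 84, kept |
| 63 | 84–98 | 8 of 15 | Day 91, kept |
| 66 | 87–101 | 5 of 15 | Day 94, dropped |
| 70 | 91–105 | 1 of 15 | Day 98, dropped |

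An exactly on-time serum is kept only when 77 ≤ d + 28 ≤ 91, that is, for d from 49 to 63.

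**Which dose-3 days are permitted.** There are two readings of the Part B Visit 04 window.

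- *Reading 1*, counted from the actual Visit 03. Section 4.2.6.1 supports this: "Study Visits 03A through 04 must be scheduled based on the date of Visit 03". Dose 3 falls 21 to 42 days after dose 2. With dose 2 on Days 21–35, dose 3 can fall on Days 42–77. On-time sera are dropped for d = 42–48 (7 days) and d = 64–77 (14 days): 21 of 36 dose-3 days.
- *Reading 2*, counted from nominal Day 56. Dose 3 can fall on Days 49–70. On-time sera are dropped for d = 64–70: 7 of 22 dose-3 days.

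With dose 2 on Day 28, both readings give Days 49–70.

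Under reading 1 there are 15 × 22 × 15 = 4950 permitted combinations of dose-2, dose-3 and serum dates. Of these, 2219 (45%) put the serum outside Days 77–91. That is a share of the calendar and not a forecast of subjects.

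**Error in the other direction.** With d = 70, sera on Days 77–90 are only 7 to 20 days after dose 3, yet they satisfy this criterion.

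**Possible loss among compliant subjects.** Assumption: timings vary independently and normally around target in whole days, truncated to the windows. Reading 1 varies the three intervals (Visits 02–03, 03–04 and 04–05), each centred on 28 days. Reading 2 centres Visit 03 on Day 28, Visit 04 on Day 56 and the 04–05 interval on 28 days, and keeps doses at least 21 days apart.

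| SD (days) | Reading 1 | Reading 2 |
|---|---|---|
| 1 | 0.0% | 0.0% |
| 2 | 3.1% | 0.8% |
| 3 | 13.6% | 6.4% |
| 4 | 22.3% | 13.4% |

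**Effect on precision.** The difference detectable with 80% power at two-sided 5% is about (1.960 + 0.842) × √(2/n) SD. At n = 1200 per arm this is 0.114, matching the 0.11 in protocol Table 8. At the largest modelled loss, n = 1200 × (1 − 0.223) ≈ 932 and the detectable difference is 0.130.

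**The case against.** The strongest reply is that the criterion names the protocol's window and that the day numbers merely illustrate it for a subject on the nominal schedule. Read that way, no compliant serum is lost. The reading is possible, but the SAP does not state it, and the parenthesis is the only numeric window given, so a programmer would be likely to code it.

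A second reply is that there are safeguards. Protocol deviations are recorded against the protocol's own windows and reviewed for PP exclusion (SAP 7.2), and all exclusions are reviewed by named roles. A serum 28 days after an in-window dose generates no deviation. This has force, because reviewers could restore such a subject. They would, however, be departing case by case from the printed days. The safeguards weigh most against the early-serum problem. A draw 7 to 20 days after dose 3 would be off schedule and a recordable deviation, so review may remove it.

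Third, the modelled losses depend on an assumed spread and on the reading chosen, and the calendar-day shares give unlikely dates the same weight as likely ones. That stands: these figures give a range, not an estimate.

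Finally, the consequence is small, because ITT and mITT immunogenicity summaries are also planned and do not use this rule. That stands too, and it limits the weight of the point without removing the contradiction.

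**Conclusion.** The concern holds. As printed, the SAP's Days 77–91 equal the protocol's Visit 05 window only when dose 3 is given on Day 56. Applied literally, they exclude subjects whose doses and Visit 05 were all in window. This is true under either reading of the Part B dose-3 window.

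The number of subjects affected cannot be derived from the documents. Under the stated timing assumption, the Part B loss is negligible at an SD of 1 day and reaches 22.3% (reading 1) or 13.4% (reading 2) at 4 days. Even the largest of these moves the detectable difference only from 0.11 to 0.13 SD. The issue is confined to the PP analysis of the secondary immunogenicity endpoint. No between-arm bias is claimed, and the primary efficacy analysis does not use the rule. It should be corrected because the rule as written gives wrong exclusions.

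**What to change.** In SAP 6.3, replace the fixed study days in the PP serum criterion with a window of 21 to 35 days after the actual date of the third administration (Visit 04), for both Parts. This restores the protocol's own 28 ± 7 days.

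As a separate tidy-up, reconcile the symptomatic-infection wording in the Table 7 and 8 shells with SAP 6.3.

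The cost is one derivation line and one wording change in the shells. The dose-3 and serum collection dates are already collected, so no new data are needed and no study procedure changes.
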